#### Analyses of the association of CIAKI with MAKE-D events

Most previous studies of outcomes following procedures that utilized iodinated contrast have focused on acute increases in SCr within days of contrast administration (CIAKI). Compared to the events that comprise our 90-day primary outcome (MAKE-D), CIAKI occurs more frequently. While some episodes of CIAKI foreshadow MAKE-D events, some do not. Our analysis of data from the VA Austin databases demonstrated that compared to patients who do not develop CIAKI following angiography, patients who develop CIAKI have a nearly four-fold increased risk of experiencing a MAKE-D event. We propose to explore this relationship by stratifying the study participants into two groups: those who do and those who do not develop CIAKI. We will then run the logistic regression model for each stratum. This analysis may reveal different levels of effectiveness of the interventions based on whether CIAKI developed. We will carry out a more global analysis using log-linear models to address the same question by adding many interaction terms without explicit stratification. We chose a sensitive definition of CIAKI based on an increase in SCr of  $\geq 0.5$  mg/dL and/or  $\geq 25\%$ . This definition has been used in most prior trials and will permit us to compare our findings with prior studies on CIAKI. Nonetheless, we will also examine the incidence of CIAKI defined by more stringent criteria (AKIN definition), evaluate the effectiveness of our interventions on the prevention of larger changes in SCr, and assess the association of CIAKI defined by greater increases in SCr with MAKE-D outcomes.

Our protocol involves administering treatment before we assess the occurrence of CIAKI. Hence, the occurrence of CIAKI cannot be viewed as a simple treatment confounder. In fact, we

hypothesize that CIAKI lies on a causal pathway leading to MAKE-D events. Therefore, the exploratory analysis based on strata defined by the development of CIAKI is the first step in confirming the presence of such a causal pathway.

The above list is not exhaustive and the study team may choose to perform additional analyses on the PRESERVE cohort within the scope of the study population, diseases of interest, and data points collected.

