## **VII. STUDY PROCEDURES**

### **A. Assessment of pre-procedure renal function**

Based on the structure of healthcare delivery within the VA Healthcare System in which patients frequently travel long distances to large VA Medical Centers for procedures such as angiograms, the SCr measured by the treating provider as part of routine clinical care prior to the procedure may be performed at a different VA laboratory than the SCr measured by the treating provider after the procedure. While an increasing majority of VA laboratories are using a standardized, IDMS-traceable method of measuring SCr, not all VA laboratories are using this calibrated methodology. Therefore, there may be inter-laboratory variation in SCr values due to differences in laboratory instrumentation and the lack of use of standardized methods of calibration. To reliably and accurately assess the development of persistent decline in kidney function (component of the primary endpoint) and CIAKI (secondary endpoint), it is essential that pre- and post-procedure SCr measurements for this purpose be standardized. We will therefore utilize a central laboratory to measure the pre-procedure study SCr and follow-up SCr values for endpoint ascertainment.

The timing of the pre-procedure study SCr (reference SCr) measurement used to assess these outcomes is also critical as the administration of IV fluids may lead to hemodilution and artifactual lowering of SCr. In addition, variation in intravascular volume status affects renal function, particularly in patients with underlying CKD. Therefore, we will standardize the timing of assessment of the reference SCr for endpoint ascertainment. This sample will be obtained following patient enrollment and immediately prior to the initiation of study IV fluids and study drug capsules to avoid any potential effects of study interventions on the baseline SCr level. This reference SCr sample will be distinct from the baseline pre-procedure SCr measured by the treating provider as part of routine clinical care that we will use to determine study eligibility. It is possible that due to expected variation in SCr levels and measurements, the baseline SCr used to determine eligibility will differ from the reference SCr such that patients who meet inclusion criteria based on the screening SCr would not have been eligible based on the reference SCr. Such patients will not subsequently be excluded or withdrawn from the study.

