## 2. Primary study outcome

The primary outcome will be a composite of serious, adverse, patient-centered events, including death, need for acute dialysis, or persistent decline in kidney function within 90 days following angiography. These outcomes, which we refer to as major adverse kidney events and death (MAKE-D) will be defined as follows:

- **Death** based on medical record and/or vital status registry documentation.
- **Need for acute dialysis** defined as the initiation of any modality of renal replacement therapy

[figure not shown]
(intermittent hemodialysis, peritoneal dialysis, continuous renal replacement therapy, or sustained low-efficiency dialysis) within 90 days of the index angiographic procedure.

- **Persistent decline in kidney function** defined by an increase in SCr from the baseline value of at least 50% at 90 days following the index angiographic procedure. This outcome will be based on a comparison of the pre-angiography and 90-day SCr values analyzed at the central laboratory.

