acute temporary dialysis following an episode of AKI. Wald et al. conducted a population-based cohort study comparing long-term outcomes of 3,769 patients who developed AKI that required temporary dialysis with 13,598 matched controls who were hospitalized, but did not develop AKI. At a median of 3 years of follow-up, the risk for ESRD was more than 3-fold higher among patients who required acute transient dialysis compared to severity of illness matched controls (adjusted HR 3.23; 95% CI: 2.70-3.86). Another study by Lo and colleagues examined the association of AKI that required transient dialysis with progression of CKD and mortality. Among 562,799 hospitalized patients who had a baseline eGFR  $\geq 45$  ml/min/1.73 m^2, 703 sustained dialysis-requiring AKI, of whom 295 (42%) died, 65 (9%) remained chronically dialysis dependent, and 343 (49%) recovered sufficient kidney function to be able to discontinue dialysis by the time of hospital discharge. In multivariate analyses, AKI requiring transient dialysis was associated with a 28-fold increased risk of developing progressive CKD, defined as a decline in kidney function to an eGFR  $\leq 30$  ml/min/1.73m^2, and a 2-fold increase risk of death over 6 years of follow up. Thus, the need for acute transient dialysis following an episode of AKI has substantial short and long-term clinical implications and represents a clinically important component of our primary composite endpoint.

*c. Justification for inclusion of persistent decline in kidney function in primary endpoint*

A series of recent studies demonstrated robust associations of CIAKI with persistent renal injury and with an acceleration in the long-term rate of decline in kidney function. We propose to include persistent renal injury at 90 days following angiography, defined by an increase in SCr from baseline of  $\geq 50\%$ , in our primary composite endpoint. In preliminary analyses, we found that the development of CIAKI following angiography was associated with a prognostically meaningful, greater than 2-fold increase in the risk of developing a  $\geq 50\%$  increase in SCr at 90 days (OR = 2.4, 95% CI 1.9-3.0) confirming the strong link between CIAKI and persistent renal injury at 90

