*d. Justification for 90-day time frame to assess the primary endpoint*

We chose to assess our primary endpoint at 90 days following angiography for two reasons. First, this represents a period of time during which adverse outcomes are more likely than not to be associated with the index angiographic procedure. Second, 90 days is commonly used in clinical practice and is proposed by the Kidney Disease: Improving Global Outcomes Foundation and the National Kidney Foundation to define the transition between acute and chronic impairment in kidney function. Therefore, persistent decline in kidney function measured at 90-days after the index angiographic procedure likely represents irreversible renal damage.

4. Secondary study outcomes

The secondary outcomes consist of:

- CIAKI defined by an increase in SCr of  $\geq 0.5$  mg/dL and/or  $\geq 25\%$  from the pre-procedure value at 4 days following angiography.
- Death within 90 days of the index angiographic procedure.

- The renal components of the primary endpoint:
  - Need for acute dialysis within 90 days of the index angiographic procedure
  - Persistent decline in kidney function at 90 days following the index angiographic procedure
- Hospitalization with acute coronary syndrome, heart failure, or cerebrovascular accident within 90 days following the index angiographic procedure. These outcomes will be defined as a primary or secondary discharge diagnosis of acute coronary syndrome (i.e., STEMI, NSTEMI, unstable angina), heart failure, or cerebrovascular accident documented in the VA electronic medical record or the hospital discharge summary obtained for non-VA hospitalizations. (This will include the occurrence of any of these events during the index hospitalization).
- All-cause re-hospitalization within 90 days of the index angiographic procedure assessed as episodes of re-hospitalization, days of hospitalization (inclusive of the index hospitalization), and hospital free days (alive and not in the hospital) through day 90.

Because AKI can occur following angiography for reasons unrelated to the administration of iodinated contrast, in a sensitivity analyses, we will also evaluate the development of CIAKI using the same threshold change in SCr, but excluding patients who experienced hypotension and/or who underwent cardiac surgery or non-cardiac vascular surgery within the 4 days following angiography.

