**E. Ascertainment of baseline kidney function**

In order to ascertain a change in kidney function, it is critical to standardize the definition of baseline kidney function. SCr often fluctuates over time because of variations in volume status, protein and salt intake, and drift in the calibration of laboratory instruments. The specific timing of the SCr used to screen patients is less critical than the value used to define the baseline SCr for endpoint ascertainment. For practical purposes, we propose to screen patients based on a SCr obtained as part of routine clinical care performed by the patient’s provider within the 30 days prior to angiography. This will not be the same pre-angiography study SCr (reference SCr) that will be used to assess the development of persistent decline in kidney function (component of the primary endpoint) or to assess the development of CIAKI (a secondary endpoint). As a result, some patients who are found to be eligible and enrolled in the study based on the eGFR calculated from the SCr performed as part of routine clinical care will subsequently have an eGFR calculated from the pre-angiography study (reference) SCr measured at the central laboratory that is  $>60$  mL/min/1.73 m^2 (diabetic patients) or  $>45$  mL/min/1.73 m^2 (non-diabetic patients). While we do not anticipate that there will be many cases in which this discrepancy occurs, patients with such differences between the screening and pre-angiography study eGFR will not be excluded as the risk of CIAKI with progressive CKD is continuous and does not increase in a step-wise fashion as transitions between CKD stages occur. For example, the risk of CIAKI for a diabetic patient with an eGFR of 61 mL/min/1.73 m^2 (i.e., stage 2 CKD) is comparable to that of a diabetic patient with an eGFR of 59 mL/min/1.73 m^2 (i.e., stage 3 CKD). Thus, we anticipate that including the small number of study patients who are deemed eligible based on their screening eGFR but whose baseline study SCr corresponds to an eGFR greater than the inclusion criteria will have minimal impact on our event rate estimates. We believe that it is critical to use a central laboratory to ascertain the reference and endpoint SCr values to minimize variation related to drift in instrument calibration. Samples for reference and endpoint ascertainment on a single patient will be run sequentially on the same analyzer to minimize issues related to drift in calibration. While this introduces issues related to sample storage, SCr is known to be stable over time in samples stored at  $-20$  °C.

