3.5. Description of the Efficacy Endpoints

3.5.1. Primary Endpoints

The primary endpoint for the study is the composite end-point assessed at 90 days post index angiographic procedure and is comprised of the 3 events described below. Those subjects with at least one of these 3 events will be considered to have the primary study endpoint.

(1) Death from all causes to be verified by medical record and/or vital status registry documentation such as the VA Beneficiary Identification and Records Locator System, the National Center for Health Statistics National Death Index database, the Social Security Administration’s Death Master File.

(2) Acute dialysis defined as the initiation of any modality of renal replacement therapy, which includes intermittent hemodialysis, peritoneal dialysis, continuous renal replacement therapy, or prolonged intermittent renal replacement therapy.

(3) Persistent decline in kidney function defined as ≥50% increase in SCr at 90 days post procedure relative to baseline SCr collected pre-Angiography procedure, and derived as follows.

$$(SCr_{day90} / SCr_{pre-procedure}) * 100\% \geq 150\%$$

Both the initial 90 day specimen and the confirmatory sample processed at the Central Lab must establish a ≥50% increase in SCr to qualify as an endpoint event.

Please note:

1. 90 day blood sample is allowed to be collected within 6month window starting 90 days post index angiographic procedure.
2. 90 day blood sample is not necessary if pt is already on dialysis at day 90 post index angiographic procedure.

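### The planned association of CIAKI with MAKE-D can be inflated, by an unknown amount, because CIAKI and persistent decline are both measured from the same single reference creatinine

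*Protocol*

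**What the plan says.** - **One reference sample.** Protocol section VII.A describes a single central-laboratory reference creatinine: "This sample will be obtained following patient enrollment and immediately prior to the initiation of study IV fluids and study drug capsules". It serves persistent decline and CIAKI alike: "The timing of the pre-procedure study SCr (reference SCr) measurement used to assess these outcomes is also critical". Section VIII.E repeats this dual use.
- **CIAKI.** Section VII.G.4 defines it as a rise of at least 0.5 mg/dL and/or 25% "from the pre-procedure value at 4 days following angiography".
- **Persistent decline.** This is a rise of at least 50%. Section VII.G.2 states: "This outcome will be based on a comparison of the pre-angiography and 90-day SCr values analyzed at the central laboratory". SAP section 3.5.1 computes the ratio "relative to baseline SCr collected pre-Angiography procedure". A second 90-day sample must confirm the rise, against the same baseline (protocol section VII.H.10.a).
- **Baseline variation.** Section VIII.E acknowledges that "SCr often fluctuates over time because of variations in volume status, protein and salt intake, and drift in the calibration of laboratory instruments". No standard deviation or coefficient of variation is given.
- **Planned analysis.** Under the heading on the association of CIAKI with MAKE-D, section XVII.E plans models stratified by CIAKI, log-linear models, and work at higher creatinine thresholds to "assess the association of CIAKI defined by greater increases in SCr with MAKE-D outcomes". The SAP specifies no analysis of this association.
- **Prior evidence.** Section VII.G.3.c reports a preliminary odds ratio of 2.4 (95% CI 1.9 to 3.0) and describes it as "confirming the strong link between CIAKI and persistent renal injury at 90" days.

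**The concern.** When two changes are measured from one baseline value, error in that value enters both with the same sign. A patient whose reference creatinine happens to be low is more likely to meet the 25% threshold on day 4 and the 50% threshold at day 90. The two outcomes are then positively associated even if contrast injury leaves no lasting effect.

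The association bears on the protocol's conceptual model, in which CIAKI lies on the path to later kidney events (sections VII.G.1 and VIII.A.1). An inflated association could be read as support for that model. A large trial would narrow the interval around the biased estimate without removing the bias.

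**Working it through.** **The plan's own figure.** There is none for this association, and the sample size is not at issue.

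**Inputs from the documents**
- CIAKI rate: 8.5% coronary and 13.2% non-coronary (protocol section III.A.1). The midpoint is (8.5 + 13.2)/2 = 10.85, taken as 10.9%.
- 90-day rates: death 1%, dialysis 5%, persistent creatinine rise 4%, any of these 8.7% (section XVII.A.2).

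**Assumed input.** s is the within-person standard deviation of a single log creatinine. Values of 0.05, 0.08 and 0.10 correspond to about 5%, 8% and 10% variation.

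**Normal model, no true link.** The two log ratios share only the baseline error, so their covariance is s². Their standard deviations are set to give the stated event rates:
- Day 4: ln(1.25)/z(10.9%) = 0.2231/1.232 = 0.181
- Day 90: ln(1.5)/z(4%) = 0.4055/1.751 = 0.232
- Correlation = s²/(0.181 × 0.232) = 0.060, 0.153 and 0.238

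At s = 0.10, persistent decline then occurs in 8.46% of patients with CIAKI and 3.45% of those without. The odds ratio is (0.0846/0.9154)/(0.0345/0.9655) = 2.58.

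| CIAKI rate | s = 0.05 | s = 0.08 | s = 0.10 |
|---|---|---|---|
| 8.5% | 1.33 | 2.04 | 2.95 |
| 10.9% | 1.28 | 1.86 | 2.58 |
| 13.2% | 1.25 | 1.74 | 2.33 |

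**Mixture models, no true link.** A minority of patients have true, mutually independent rises at day 4 and day 90, every draw carries noise, and the confirmatory sample is included. Across several assumed injury sizes the spurious odds ratio was 1.00–1.24, 1.00–1.70 and 1.03–2.04 at 5%, 8% and 10% variation. With a separate, independent baseline for each rise it was 0.99–1.01, which isolates the shared baseline as the cause.

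**Composite.** At most 4/8.7 = 46% of MAKE-D events involve the creatinine criterion, and at least (8.7 − 6)/8.7 = 31% qualify through it alone. Add an independent 4.9% risk of death or dialysis, so that 1 − 0.96 × 0.951 = 8.7%. At s = 0.10 in the normal model, MAKE-D risk is 1 − 0.9154 × 0.951 = 12.95% with CIAKI and 1 − 0.9655 × 0.951 = 8.18% without, an odds ratio of 1.67. At s = 0.05 it is 1.13. One mixture model gave 1.00 at s = 0.05 and 1.12 at s = 0.10.

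**Checking a remedy.** Using the mean of screening and reference creatinine as the 90-day denominator still leaves half the reference error in it, so the covariance is s²/2. With a 10% CIAKI rate and s = 0.10, the normal-model odds ratio falls only from 2.71 to 1.67. Screening creatinine alone removes the shared error if its own error is independent. If the two errors correlate at 0.5, it also leaves about 1.67.

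**The case against.** **Existing safeguards.** The reference draw is timed before study fluids (VII.A). A known change of 25% or more over the preceding 3 days is an exclusion (VI.A.2). Reference and endpoint samples run in sequence on one analyzer (VIII.E). These reduce baseline error. They do not remove biological fluctuation or the shared denominator, and the confirmatory draw repeats only the numerator.

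**Size.** Every magnitude rests on an assumed variation. The high values come from the normal model, and mixture models can be close to null even at 10%. The calculation uses the standard CIAKI threshold, whereas the quoted analysis also covers larger rises. This stands in full: the inflation may be negligible.

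**Status.** The analysis is exploratory and absent from the SAP. Section VIII.A.1 already allows that CIAKI may only mark underlying disease. That caveat concerns confounding, not measurement, but it does show caution about the causal reading.

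**Stronger readings that the documents do not support**
- A reader might infer that baseline noise explains persistent decline. In one mixture model with noise only at 10% variation, confirmed rises of at least 50% occurred in 0.015% of patients, against the 4% assumed.
- A reader might infer that the preliminary odds ratio of 2.4 is an artefact, since the normal model reaches it near 10% variation. The documents do not say which baseline that analysis used.
- A reader might attach to the quoted association the statement in XVII.E about a first step in confirming a causal pathway. That statement concerns the CIAKI-stratified treatment analysis.

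**Conclusion.** The point holds as a minor one. As planned, the association of CIAKI with MAKE-D includes a component produced by the shared reference creatinine, and no planned step separates it out. The direction is upward. The size cannot be determined from the documents: with no true link, the odds ratio for persistent decline is about 1.0–1.3, 1.0–2.0 and 1.0–2.95 at assumed variations of 5%, 8% and 10%, and smaller for MAKE-D. These ranges assume CIAKI rates of 8.5% to 13.2%, a 4% rate of persistent decline, and independent true changes at day 4 and day 90.

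A reader might extend this to the primary result, but that does not follow. The reference sample precedes study treatment, so its error is balanced by randomisation. The treatment comparisons, type I error and sample size are unaffected.

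**What to change.** In protocol section XVII.E, or in a matching SAP paragraph:

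1. Report the CIAKI association separately for death or dialysis, which use no baseline creatinine, and for persistent decline.
2. As a sensitivity analysis, repeat the persistent-decline association with the screening creatinine alone as the 90-day denominator, keeping the reference value for CIAKI. Do not use the mean of the two. State the limits: the screening value usually comes from a local laboratory, was selected by the eGFR cut-off, and may share the patient's volume state at the reference draw.
3. State that the composite association will not by itself be presented as evidence that CIAKI leads to persistent decline.

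The cost is a few sentences and a few exploratory models on data already collected. The drawbacks are fewer events in item 1 and a noisier baseline in item 2.

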## **II. STUDY HYPOTHESES AND OBJECTIVES**

### **A. Study hypotheses**

1. Compared to peri-procedural infusion of IV isotonic saline, peri-procedural infusion of IV isotonic sodium bicarbonate will decrease 90-day morbidity (i.e., need for acute dialysis, persistent decline in kidney function) and mortality in high-risk patients undergoing coronary or non-coronary angiography. The decrease in 90-day morbidity and mortality associated with sodium bicarbonate administration in high-risk patients will be mediated by a reduction in the incidence of contrast-induced acute kidney injury within 4 days of angiography.
  
2. Administration of NAC in the peri-procedural period will decrease 90-day morbidity (i.e., need for acute dialysis, persistent decline in kidney function) and mortality in high-risk patients undergoing coronary or non-coronary angiography. The decrease in 90-day morbidity and mortality associated with NAC administration in high-risk patients will be mediated by a reduction in the incidence of contrast-induced acute kidney injury within 4 days of angiography.

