Despite the abundance of epidemiological and experimental data associating small changes in SCr with adverse renal and extra-renal outcomes, the evidence remains inadequate to warrant the use of small changes in SCr as a surrogate primary endpoint in large transformative clinical trials. Although serious, downstream events following angiography occur as a consequence of CIAKI, they may also develop independent of this intermediate event, as many of the clinical conditions that predispose patients to the development of CIAKI (e.g., CKD, diabetes mellitus, heart failure) are also independently associated with mortality and other adverse outcomes (Figure 2). In

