## V. OVERVIEW OF STUDY DESIGN

The proposed comparative effectiveness study is a multicenter, randomized, double-blind clinical trial that will use a 2 x 2 factorial design to assess the effectiveness of IV isotonic sodium bicarbonate compared to IV isotonic saline and NAC compared to placebo for the prevention of serious, adverse, patient-centered outcomes in high-risk patients undergoing coronary or non-coronary angiography. The primary hypotheses to be tested are that isotonic bicarbonate is more effective than saline and that NAC is more effective than placebo for the prevention of serious morbidity and mortality following coronary and non-coronary angiography in high-risk Veterans. Each of these two hypotheses are of equal importance as there is clinical equipoise on both the comparative effectiveness of bicarbonate and saline and the benefit of NAC. Moreover, despite the lack of any data establishing the efficacy of NAC in the absence of concomitant IV fluids, our data indicate that as many as 12% of high-risk Veterans receive this anti-oxidant in lieu of any IV fluids (*vide supra*). We believe that the beneficial effects of these interventions on adverse outcomes will be mediated through a reduction in the development of CIAKI.

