## **G. Study Outcomes**

### **1. Conceptual basis for study outcomes**

Nearly all clinical trials of IV fluid and NAC for the prevention of CIAKI utilized the surrogate endpoint of change in SCr within 2 to 5 days of contrast administration and were not designed or powered to test the hypothesis that these interventions prevent serious, adverse downstream outcomes. While there is a strong association between small changes in SCr within days of angiography and adverse downstream outcomes, not all episodes of CIAKI lead to serious downstream events (Figure 4). For this reason, the primary objective of this trial is to evaluate whether bicarbonate (as compared to saline) and NAC (as compared to placebo) reduce the incidence of serious, adverse patient-centered outcomes. We postulate that the beneficial effects of bicarbonate and NAC on adverse downstream outcomes will be mediated specifically by means of a reduction in the incidence of CIAKI.

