#### **E. Additional exploratory analyses**

We will explore several other hypotheses related to the binary 90 day MAKE-D outcome:

1. The combination of bicarbonate and NAC (interaction term) is more effective than bicarbonate or NAC alone.
2. (Per Protocol analysis) Bicarbonate, NAC, and their combination reduce the incidence of the primary outcome, MAKE-D, among subjects who received the full dose of bicarbonate.
3. (Per Protocol analysis) Bicarbonate, NAC, and their combination reduce the incidence of the primary outcome, MAKE-D, among subjects who received the full course of NAC.
4. Bicarbonate, NAC, and their combination reduce the incidence of the individual components of MAKE-D, each treated as a separate outcome: death, need for acute dialysis, and persistent decline in kidney function.
5. Bicarbonate, NAC, and their combination reduce the incidence of each of the individual cardiovascular components of the secondary outcome; namely acute coronary syndrome, heart failure, and cerebrovascular accident.
6. Bicarbonate, NAC, and their combination result in a greater reduction in the incidence of MAKE-D outcomes in subjects who develop CIAKI compared to those who do not develop CIAKI.
7. Bicarbonate, NAC, and their combination increase the mean number of days that participants are alive and hospitalization free (hospital free days) in the 90 days after angiography.

8. The benefits of bicarbonate, NAC, and their combination on MAKE-D outcomes are independent of the volume and rate of fluid administration above the minimum values prescribed in the protocol.

This brief list entails a large number of analyses. However, the sample size is large and the implicit hypotheses are highly inter-correlated. Thus, we anticipate that we can use a significance level of 1% ( $p = 0.01$ ) to detect associations of potential clinical importance in these exploratory analyses.

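### Fitting the treatment model separately in patients with and without CIAKI cannot show that benefit is mediated through CIAKI

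*Protocol*

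**What the plan says.** Protocol II.A attaches a mechanism to each of the two hypotheses: the fall in 90-day morbidity and mortality "will be mediated by a reduction in the incidence of contrast-induced acute kidney injury within 4 days of angiography". Section V repeats the belief, and VII.G.1 narrows it to benefit "mediated specifically by means of a reduction in the incidence of CIAKI".

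The analysis meant to examine this is in Protocol XVII.E, under the heading on the association of CIAKI with MAKE-D. Patients are divided by whether CIAKI developed, and "We will then run the logistic regression model for each stratum". The expected yield is that "This analysis may reveal different levels of effectiveness of the interventions based on whether CIAKI developed". A log-linear model with interaction terms is added for the same question. The section recognises that CIAKI arises after treatment and is not an ordinary confounder, and it concludes that the exploratory analysis based on "strata defined by the development of CIAKI is the first step in confirming the presence of such a causal pathway".

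Item 6 of the exploratory list in XVII.E is that the interventions "result in a greater reduction in the incidence of MAKE-D outcomes in subjects who develop CIAKI compared to those who do not develop CIAKI". Exploratory analyses are judged at the 1% level.

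The SAP compares CIAKI between arms as a secondary endpoint (3.5.2 and 5.4). It contains no CIAKI-stratified analysis of MAKE-D and no mediation analysis.

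**The concern.** Mediation means that treatment lowers the risk of CIAKI and that having less CIAKI lowers the risk of MAKE-D. Once patients are grouped by CIAKI status, that route is closed, and any treatment effect left within a group must come by another route or from bias. A treatment effect inside a CIAKI stratum is therefore not evidence for the pathway. A larger effect in one stratum than in the other, as item 6 expects, is effect modification, which is a different question.

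CIAKI status is also known only after randomisation. Patients with CIAKI in one arm need not resemble patients with CIAKI in the other. Protocol III.A.2.e says that conditions predisposing to CIAKI, such as kidney disease, diabetes and heart failure, "are also independently associated with mortality and other adverse outcomes". The plan for this analysis names no adjustment for them.

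At stake is the trial's answer to a question it treats as central: whether preventing small creatinine rises prevents outcomes that matter to patients. Protocol VIII.A.1 says that a separation of the two would itself be an important finding.

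**Working it through.** The documents give no figure for this analysis, so there is nothing to reproduce first. The check asks what the planned strata would show if the protocol's own pathway were exactly true.

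**Inputs from the protocol**
- Control MAKE-D rate: 8.7% (XVII.A.2).
- CIAKI incidence: 13.2% after non-coronary and 8.5% after coronary angiography (III.A.1).
- MAKE-D risk with CIAKI against without: nearly four-fold (XVII.E), taken here as a causal risk ratio of 4.
- Effect of treatment on CIAKI: relative risk 0.62, the pooled figure for bicarbonate (XVII.A.2).

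**Step 1. Complete mediation, no common causes**
- Risk without CIAKI: r = 0.087 / (1 + 3 × 0.132) = 0.0623. Risk with CIAKI: 4r = 0.2493.
- CIAKI under treatment: 0.132 × 0.62 = 0.0818.
- MAKE-D under treatment: 0.0623 × (1 + 3 × 0.0818) = 0.0776.
- Overall OR: (0.0776/0.9224) / (0.0870/0.9130) = 0.88.
- With CIAKI, the risk is 24.9% in both arms: OR 1.00. Without CIAKI, it is 6.2% in both arms: OR 1.00.

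With the coronary figure of 8.5%, r = 0.0693, MAKE-D falls from 8.70% to 8.03% (OR 0.92), and both stratum ORs are again 1.00. At 13.2% incidence, a CIAKI reduction of about 88% would deliver the full planned 25% fall in MAKE-D (overall OR 0.73), and both stratum ORs would still be 1.00.

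**Step 2. Complete mediation with a common cause**

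Assumed for illustration, not taken from the documents: a trait present in 20% of patients that doubles the risk of CIAKI and, separately, of MAKE-D, with CIAKI tripling MAKE-D risk. Overall CIAKI and MAKE-D in controls stay at 13.2% and 8.7%. This gives CIAKI risks of 11% without the trait and 22% with it, and a baseline MAKE-D risk of 0.087/1.552 = 0.0561 (no trait, no CIAKI). In controls with CIAKI, the trait share is 0.2 × 0.22 / (0.8 × 0.11 + 0.2 × 0.22) = 33.3%, and their MAKE-D risk is 0.0561 × 3 × 1.333 = 22.4%.

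| Where treatment cuts CIAKI by 38% | Overall MAKE-D, treated | Overall OR | Trait share among treated with CIAKI | OR with CIAKI | OR without CIAKI |
|---|---|---|---|---|---|
| All patients equally | 7.95% | 0.91 | 33.3% | 1.00 | 1.01 |
| Only patients without the trait | 8.33% | 0.95 | 44.6% | 1.11 | 0.99 |
| Only patients with the trait | 8.33% | 0.95 | 23.7% | 0.91 | 1.01 |

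The last two rows have the same overall benefit, obtained wholly through CIAKI, yet the CIAKI-stratum OR lies on opposite sides of 1.

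A wider grid used trait prevalence of 20% or 40%, risk ratios of 2 to 4 on CIAKI and 2 or 4 on MAKE-D, CIAKI tripling MAKE-D risk, and CIAKI cut by 38% or 80%, either uniformly or in one trait group only. Under complete mediation the OR ran from about 0.52 to 1.93 in the CIAKI stratum and from 0.97 to 1.11 in the other. These are ranges under assumptions, not predictions for this trial.

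**The case against.** The protocol calls this analysis exploratory and a first step, and it knows that CIAKI follows treatment. A reader might infer that the plan would declare mediation absent if both strata were null. The documents contain no such rule, and an overall effect with null strata is a pattern that fits mediation. That stands. But the protocol does not name this as the pattern to look for, item 6 looks for another one, and with common causes null strata are not a reliable signature either.

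A reader might also infer that a beneficial treatment would look harmful among patients with CIAKI because treated patients who still develop it are frailer. The documents do not support a direction. With a uniform CIAKI relative risk of 0.62 and an assumed frailty in 30% of patients that raises both risks three- or four-fold, the CIAKI-stratum OR is 1.00 and the other is 1.02 to 1.04. Apparent harm needs a non-proportional effect on CIAKI, and an opposite pattern of effect gives apparent benefit.

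The exact value of 1.00 requires the yes/no threshold to carry the whole pathway. Protocol III.A.2.c reports graded risk with CIAKI severity. If treatment also softens injuries that still cross the threshold, a benefit within the CIAKI stratum would fit a kidney-injury pathway. Item 6 is then a coherent question, and it is listed separately from the pathway analysis. It still compares groups formed after randomisation.

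Parts of a better analysis are already planned. The effect of treatment on CIAKI is a secondary endpoint, stricter CIAKI definitions will be examined, the list of analyses is expressly open, and a log-linear model could test whether treatment and MAKE-D are independent given CIAKI. None of these, as described, estimates an indirect effect or adjusts for common causes.

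**Conclusion.** The concern holds in this form: the CIAKI-stratified models, and the pattern sought in item 6, cannot confirm that benefit runs through CIAKI. Under the protocol's own pathway with no common causes, a fall in MAKE-D from 8.70% to 7.76% (OR 0.88) would accompany ORs of 1.00 in both strata. This rests on a binary mediator, 13.2% CIAKI, a causal four-fold risk and a CIAKI relative risk of 0.62; the null strata do not depend on the particular values. With common causes the stratum ORs can mislead in either direction, by an amount that the documents do not allow one to fix.

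The consequence is limited. The analysis is exploratory and outside the SAP, and it affects no primary or secondary result, sample size or stopping decision. It is worth correcting because mediation is written into both study hypotheses.

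**What to change.** In Protocol XVII.E and in the SAP, replace the CIAKI-stratified models as the test of the pathway with an exploratory mediation analysis:

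- Estimate the effect of each treatment on CIAKI.
- Model MAKE-D on treatment, CIAKI, their interaction and prespecified baseline common causes.
- Report indirect and direct effects with bootstrap intervals, and a sensitivity analysis for unmeasured confounding between CIAKI and MAKE-D.
- State the limits. Hypotension, surgery and repeat contrast arise after the procedure and may themselves be affected by treatment, in which case natural direct and indirect effects are not identified without further assumptions. A yes/no CIAKI threshold may miss part of the pathway.

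Keep item 6 only if it is relabelled as descriptive, and as neither evidence for mediation nor a randomised comparison.

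The cost is a little more analysis on data already to be collected, and assumptions that cannot be tested and must be stated.
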